SPONSOR: The sponsor is responsible for ensuring before a study begins that arrangements are in place for the research team to access resources and support to deliver the research as proposed and allocate responsibilities for the management, monitoring and reporting of the research. The Sponsor also has to be satisfied there is agreement on appropriate arrangements to record, report and review significant developments as the research proceeds, and approve any modifications to the design.

FUNDER: The funder is the entity that will provide the funds (financial support) for the conduction of the study. Funders are expected to provide assistance to any enquiry, audit or investigation related to the funded work. If further arrangements have been agreed with the funder, please refer to the funding agreement and insert

CHIEF INVESTIGATOR (CI): The person who takes overall responsibility for the design, conduct and reporting of a study. If the study involves researchers at more than once site, the CI takes on the primary responsibility whether or not he/she is an investigator at any particular site.

The CI role is to complete and to ensure that all relevant regulatory approvals are in place before the study begins. Ensure arrangements are in place for good study conduct, robust monitoring and reporting, including prompt reporting of incidents, this includes putting in place adequate training for study staff to conduct the study as per the protocol and relevant standards.

The Chief Investigator is responsible for submission of annual reports as required. The Chief Investigator will notify the R&I Office of the end of the study, including the reasons for the premature termination. Within one year after the end of study, the Chief Investigator will submit a final report with the results, including any publications/abstracts to the REC.

PRINCIPAL INVESTIGATOR (PI): Individually or as leader of the researchers at a site; ensuring that the study is conducted as per the approved study protocol, and report/notify the relevant parties – this includes the CI of any breaches or incidents related to the study.

OTHER: add other key personal/entity responsibilities where relevant to the study

DECLARATIONS

IRAS Project ID: **227870**

11. [name] (SpR Anaesthesia)

12. [name] (ICU Clinical Fellow)

STUDY SUMMARY

STUDY OVERVIEW	
Full title	The impact of systemic pH on cardiac function and clinical outcome in the critically ill patient
Objectives	Hypothesis Titration studies in animals with normal cardiac function show that a reduction in blood pH (and presumably that of the intracellular and interstitial compartments) from the normal level of 7.40 to 7.20 is associated with a rise in cardiac output. However, when blood pH is less than 7.20, cardiac output is reduced. Similar studies in humans with or without normal cardiac function have not been done, and yet blood pH at which aggressive treatment is recommended has been set at 7.20 based solely on animal experiments. We hypothesize that a change in blood pH in humans will also affect cardiac function, but the level of blood pH at which this is observed might be similar or different in humans. In addition, the presence or absence of

Full title of the research: **The impact of systemic pH on cardiac function and clinical outcome in the critically ill patient.**

IRAS Project ID: **227870**

	
underlying cardiac disease and the type of acid-base abnormality present might modify the response of the heart to changes in blood pH.
 
Goals
 
Primary
 
 1. Assess whether there are significant changes in cardiac function associated with changes in blood pH. 2. Relate the changes in cardiac function to presence or absence of underlying cardiac disease. 
Secondary
 
 3. To establish which factors affected by blood pH have an impact on cardiac function. 4. Study the mortality of patients admitted to the Intensive Care Unit (ICU) who had continuous cardiac monitoring at any time during their admission and relate it to changes in blood pH.
Type of trial	It is not a trial
Trial design and methods	It is not a trial
Health condition(s) or problem(s) studied	It is not a trial
Target sample size	Taking into account that the primary objective of the study is to

Full title of the research: **The impact of systemic pH on cardiac function and clinical outcome in the critically ill patient.**

IRAS Project ID: **227870**

	analyze the relationship between the quantitative variables: change in pH and change in Cardiac Contractility, assuming an alpha risk of 5% (95% confidence level), a 20% beta risk (power of 80%) and a minimum ratio that has an estimated clinical significance with a correlation coefficient of 1.5, a bilateral estimate of sample size of 346 subjects is obtained. Assuming a 5% loss (17 individuals) during the study a total of 363 cases would be necessary.
Trial design and methods	It is not a trial
Trial duration per participant:	It is not a trial
Main inclusion/exclusion criteria:	
EXCLUSION CRITERIA
 
 • Atrial or ventricular arrhythmia: you need a stable pulse to measure the contour. • Aortic, mitral or tricuspid valve insufficiency. In the case of valve insufficiency the valve does not close correctly. Therefore, the thermodilution curve is affected by indicator regurgitation, resulting in a prolonged indicator decay time. • Intra-Aortic Balloon pump: once again, the pulse contour is all wrong; but you can still get thermodilution cardiac output measurements. • Aortic aneurysm: the contour will be bizarre because the arterial compliance is going to be weird, with the aortic aneurysm acting as a damping system by absorbing all the pressure wave. • Extracorporeal circuit: when you are on bypass, there is no real arterial waveform • Pneumonectomy: PiCCO relies on there being a relatively normal pulmonary vasculature. • Massive pulmonary embolism: as above; it is essentially a pneumonectomy by embolism. • Intracardiac shunt: the PA catheter will also give an inaccurate thermodilution reading. • Less than a minimal tidal volume 6-

Full title of the research: **The impact of systemic pH on cardiac function and clinical outcome in the critically ill patient.**

IRAS Project ID: **227870**

	
8mL/kg
 
• NON-positive pressure ventilated patients:
➤ Why does Stroke Volume Variation only apply to positive pressure ventilated patients? It still applies in spontaneously breathing patients; however it is a poorer predictor of fluid responsiveness.➤ Why? The sensitivity is decreased: its only 63%. The spontaneous breathing efforts draw a smaller tidal volume, and from such minor changes in thoracic pressure there would insufficient change in ventricle loading; so there may still be changes to stroke volume, but they would be tiny and difficult to measure.➤ - If there is profound hypovolemia, the IVC can collapse on inspiration. Obviously this decreases preload, and confuses your SVV. You cannot predict fluid responsiveness this way, because you never get an accurate impression of preload.➤ - In spontaneous respiration, inspiration increases the right ventricular preload, which means the right ventricular filling is likely still appear adequate even if there is some hypovolemia. In spite of low overall volume, the right ventricular preload remains adequate, and thus at least one of the ventricles is likely to be operating in the
--	---

Full title of the research: **The impact of systemic pH on cardiac function and clinical outcome in the critically ill patient.**

IRAS Project ID: **227870**

	
preload-independent straight part of the Frank-Starling curve
 
 • Severe obesity: In obese patients, Extravascular Lung Water Index (EVLWI) is underestimated because it is related to the body weight.

Statistical methodology and analysis:
	
Statistical methods
 
The description of quantitative variables is carried out with central tendency and dispersion indices, whether based on values (mean and standard deviation) or on ordinations (median and interquartile range) according to whether they meet normality or not, respectively. Its graphic representation is done with Histograms and Cash Diagrams. The description of categorical variables is performed with absolute and relative frequencies in percentages. Its graphic representation is done with bar charts.
 
The relationship between categorical variables is analyzed by comparing proportions with the Pearson Chi-square test, provided that there are less than 20% of squares in the contingency table with expected frequencies less than 5. In the case that there is more 20% of squares with expected frequencies less than 5, the Fisher's exact test is used bilaterally.

Full title of the research: **The impact of systemic pH on cardiac function and clinical outcome in the critically ill patient.**

IRAS Project ID: **227870**

	
The magnitude of the effect of the relationship between two binary variables has been analyzed with the Ratios of proportions or Relative Risk and with the Odds Ratio.
 
The relationship between a binary exposure variable and a quantitative response is analyzed with the Student-Fisher t test for independent samples if the normality condition is met. According to whether or not the equality of variances are met, the Student-Fisher t test is used for independent groups for homogeneous variances or for non-homogeneous variances, respectively. In case of not fulfilling the condition of normality, the comparison of two means is made with the non-parametric Mann-Whitney U test.
 
The comparison between a polytomic predictor and a quantitative response is made through the analysis of variance (ANOVA) in the case of meeting the conditions of normality and homogeneity of variances. If any of these conditions is not met, it is done with the non-parametric H test of Kruskal-Wallis. If the polytomic predictor is ordinal, the ANOVA trend test or the non-parametric Jonckheere-Terpstra trend test is also used, depending on whether normality is met or not, respectively.

--	---

Full title of the research: **The impact of systemic pH on cardiac function and clinical outcome in the critically ill patient.**

IRAS Project ID: **227870**

	
The relationship between two independent quantitative variables is evaluated with the correlation coefficient r of Pearson if normality is met, or with the nonparametric correlation coefficient ρ of Spearman if normality is not met. Its graphic representation is made with the scatter diagrams or points.
 
Normality is assessed with the Kolmogorov-Smirnov test with the Lilliefors significance correction for large samples, or with the Shapiro-Wilks test for small samples. The equality of variances is analyzed with the Levene variance homogeneity test.
 
The relationship between two related quantitative variables is performed using the Student-Fisher t-test for related samples in case the normality condition is met. Otherwise, the non-parametric Wilcoxon T test is used. The relationship between two paired categorical variables is performed by the McNemar symmetry test.
 
The relationship between a continuous quantitative response and one or several predictors, whether binary, polytomic or quantitative, is done with Simple or Multiple Linear Regression

--	---

Full title of the research: **The impact of systemic pH on cardiac function and clinical outcome in the critically ill patient.**

IRAS Project ID: **227870**

	
respectively.
 
The polytomous predictors variables are introduced in the Linear Regression models broken down into binary indicator variables coded with respect to the first reference category.
 
An estimative multivariate linear regression model of the effect of the predictor Change of pH (between the lowest and highest pH) on the response Change in cardiac output (corresponding to the moments between the lowest and the highest pH) has been performed. The possible role as confounding factors of several variables on this relationship has been evaluated. A predictive multivariate model of linear regression has been performed to evaluate the factors that intervene in the Cardiac Contractility.
 
Both the predictive and the estimative models have been carried out with the manual backward step procedure using the criterion of decreasing statistical significance to establish the order to evaluate the withdrawal or permanence of each predictor.
 
In the multivariate predictive linear regression model, the criterion of statistical significance was used to decide the maintenance or withdrawal of the predictors in each step. They

--	--

Full title of the research: **The impact of systemic pH on cardiac function and clinical outcome in the critically ill patient.**

IRAS Project ID: **227870**

	
remain in the model if they are significant and are removed from the model if they are not significant.
 
In the multivariate models of linear regression, the criterion of clinical significance has been used to decide on the maintenance or withdrawal of the predictors in each step. They remain in the model if they produce a change greater than 10% in the coefficient of the predictor of interest (presence of confounding bias) and withdraw if the change is less than 10% (absence of confounding bias).
 
The conditions of application of the simple or multiple linear regression (linearity, independence, normality and equality of variances) are evaluated by analysing the residuals.
 
Values of $P < 0.05$ are considered significant. The statistical treatment has been performed the statistical package SPSS, version 18 (SPSS Inc, Chicago, IL, USA).

STUDY TIMELINES	
Study Duration/length	Approximately 6 months
Expected Start Date	April 2018
End of Study definition and	Expected on November 2018

Full title of the research: **The impact of systemic pH on cardiac function and clinical outcome in the critically ill patient.**

IRAS Project ID: **227870**

anticipated date	
Key Study milestones	March study submission April 2018 start of data collection October –November data analysis
STORAGE of SAMPLES (if applicable)	No applicable
Human tissue samples	No applicable
Data collected / Storage	Observational data will be completely anonymous before digital storage and sending for analysis. Previous to that, it will be collected on paper form which will be encrypted coded.

1 INTRODUCTION

Why?

We would like to perform an analysis of the relationship between systemic pH and cardiac function and clinical outcome in critically ill patients in patients hospitalized the Intensive Care Unit.

How is it of relevance and importance to patients and public?

Studying this subject we could provide important information about the impact of systemic pH on cardiac function and clinical outcome in seriously ill patients and enable the clinician to

Full title of the research: **The impact of systemic pH on cardiac function and clinical outcome in the critically ill patient.**

IRAS Project ID: **227870**

understand the best treatment of these patients. Patients will be studied who had cardiac monitoring during their ICU admission and an acid-base metabolic disorder. We exclude those patients with cardiac history or who presented an acute coronary syndrome during ICU admission.

IT IS NOT A THERAPEUTIC STUDY. ONLY OBSERVATIONAL. NO INTERVENTIONS.

Where?

In seven different ICU's between King's College NHS Foundation Hospital and Lewisham and Greenwich NHS Trust

How?

The study will take approximately six month to collect prospectively data from each unit. The data will be extracted from the medical notes and ICU charts. No active involvement with participants.

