2 BACKGROUND AND RATIONALE

3 OBJECTIVES

Goals

Primary

1. Assess whether there are significant changes in cardiac function associated with changes in blood pH.
2. Relate the changes in cardiac function to presence or absence of underlying cardiac disease.

Secondary

3. To establish which factors affected by blood pH have an impact on cardiac function.

Full title of the research: **The impact of systemic pH on cardiac function and clinical outcome in the critically ill patient.**

IRAS Project ID: **227870**

4. Study the mortality of patients admitted to the Intensive Care Unit (ICU) who had continuous cardiac monitoring at any time during their admission and relate it to changes in blood pH.

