4 STUDY DESIGN

- Study population and groups: those patients on haemodynamic monitoring in ICU (PiCCO monitoring)
- **Calculation of the sample size:**

Taking into account that the primary objective of the study is to analyze the relationship between the quantitative variables: change in pH and change in Cardiac Contractility, assuming an alpha risk of 5% (95% confidence level), a 20% beta risk (power of 80%) and a minimum ratio that has an estimated clinical significance with a correlation coefficient of 1.5, a bilateral estimate of sample size of 346 subjects is obtained. Assuming a 5% loss (17 individuals) during the study a total of 363 cases would be necessary.

- **Statistical methods:**

The description of quantitative variables is carried out with central tendency and dispersion indices, whether based on values (mean and standard deviation) or on ordinations (median and interquartile range) according to whether they meet normality or not, respectively. Its graphic representation is done with Histograms and Cash Diagrams. The description of categorical variables is performed with absolute and relative frequencies in percentages. Its graphic representation is done with bar charts.

Full title of the research: **The impact of systemic pH on cardiac function and clinical outcome in the critically ill patient.**

IRAS Project ID: **227870**

The relationship between categorical variables is analyzed by comparing proportions with the Pearson Chi-square test, provided that there are less than 20% of squares in the contingency table with expected frequencies less than 5. In the case that there is more 20% of squares with expected frequencies less than 5, the Fisher's exact test is used bilaterally.

The magnitude of the effect of the relationship between two binary variables has been analyzed with the Ratios of proportions or Relative Risk and with the Odds Ratio.

The relationship between a binary exposure variable and a quantitative response is analyzed with the Student-Fisher t test for independent samples if the normality condition is met. According to whether or not the equality of variances are met, the Student-Fisher t test is used for independent groups for homogeneous variances or for non-homogeneous variances, respectively. In case of not fulfilling the condition of normality, the comparison of two means is made with the non-parametric Mann-Whitney U test.

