7.1 Inclusion Criteria

- Over 16 years old- 65 years old
- On cardiac monitoring (PiCCO device)

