7.2 Exclusion Criteria

EXCLUSION CRITERIA

Full title of the research: **The impact of systemic pH on cardiac function and clinical outcome in the critically ill patient.**

IRAS Project ID: **227870**

- **Atrial or ventricular arrhythmia:** you need a stable pulse to measure the contour.
- **Aortic, mitral or tricuspid valve insufficiency.** In the case of valve insufficiency the valve does not close correctly. Therefore, the thermodilution curve is affected by indicator regurgitation, resulting in a prolonged indicator decay time.
- **Intra-Aortic Balloon pump:** once again, the pulse contour is all wrong; but you can still get thermodilution cardiac output measurements.
- **Aortic aneurysm:** the contour will be bizarre because the arterial compliance is going to be weird, with the aortic aneurysm acting as a damping system by absorbing all the pressure wave.
- **Extracorporeal circuit:** when you are on bypass, there is no real arterial waveform
- **Pneumonectomy:** PiCCO relies on there being a relatively normal pulmonary vasculature.
- **Massive pulmonary embolism:** as above; it is essentially a pneumonectomy by embolism.
- **Intracardiac shunt:** the PA catheter will also give an inaccurate thermodilution reading.
- **Less than a minimal tidal volume 6-8mL/kg**
- **NON-positive pressure ventilated patients:**
 - **Why does Stroke Volume Variation only apply to positive pressure ventilated patients?** It still applies in spontaneously breathing patients; however it is a poorer predictor of fluid responsiveness.
 - **Why? The sensitivity is decreased: its only 63%.** The spontaneous breathing efforts draw a smaller tidal volume, and from such minor changes in thoracic pressure there would insufficient change in ventricle loading; so there may still be changes to stroke volume, but they would be tiny and difficult to measure.
 - **- If there is profound hypovolemia, the IVC can collapse on inspiration.** Obviously this decreases preload, and confuses your SVV. You cannot predict fluid responsiveness this way, because you never get an accurate impression of preload.
 - **- In spontaneous respiration, inspiration increases the right ventricular preload,** which means the right ventricular filling is likely still appear adequate even if there is some hypovolemia. In spite of low overall volume, the right ventricular preload remains adequate, and thus at least one of the ventricles is likely to be

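### Section 1 excludes patients with a cardiac history, but primary objective 2 compares patients with and without cardiac disease, and section 7 does not list the exclusion

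*Combined protocol and SAP*

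**What the plan says.** Section 1 (Introduction) gives an explicit exclusion: "We exclude those patients with cardiac history or who presented an acute coronary syndrome during ICU admission". The same paragraph limits the study to patients with a metabolic acid-base disturbance.

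The second of the two primary objectives, in the Study Summary and in section 3, is to "Relate the changes in cardiac function to presence or absence of underlying cardiac disease". The hypothesis in the Study Summary goes further and says that "underlying cardiac disease and the type of acid-base abnormality present might modify the response of the heart to changes in blood pH".

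The parts of the protocol that set eligibility do not repeat the section 1 rule:

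- Section 4 describes the population as "those patients on haemodynamic monitoring in ICU (PiCCO monitoring").
- Section 7.1 asks for an age range and "On cardiac monitoring (PiCCO device").
- Section 7.2 and the summary criteria list conditions that disturb the PiCCO reading. These include "Atrial or ventricular arrhythmia" and "Aortic, mitral or tricuspid valve insufficiency", but not cardiac history or acute coronary syndrome.
- The daily screening rule in section 7 (Recruitment) mentions only PiCCO monitoring.

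The data form printed under section 20 records ischaemic heart disease, heart failure and cardiac devices, and has an admission category for cardiogenic shock. Section 8 describes a generic two-group test for a binary exposure. It also describes a regression of change in cardiac output on change in pH, with unnamed covariates handled as possible confounders under a 10% change-in-coefficient rule.

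**The concern.** A comparison of patients with and without cardiac disease needs both groups. If section 1 is followed, the cardiac-disease group has few or possibly no patients, and a primary objective cannot be reliably estimated. Analysis cannot repair this, because patients who were never enrolled have no data.

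If section 7 is followed, objective 2 as worded can be estimated, but section 1 then misdescribes the cohort. Screening is done by a researcher in each of seven ICUs. If they read different sections, the case mix will differ by site.

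The secondary concern is about the question asked. The hypothesis is that cardiac disease changes the response to pH, which is a difference in slopes. A two-group test of the change in cardiac function can be positive only because the two groups had different pH changes, and that could be misread as a different response to pH.

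**Working it through.** **Setting the passages side by side**

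| Place | Patients with cardiac history |
|---|---|
| Section 1 | Excluded |
| Primary objective 2 (Summary, section 3) | Needed as one of two groups |
| Hypothesis (Summary) | Needed |
| Summary criteria, section 4, 7.1, 7.2, screening rule | Exclusion not listed |
| Data form (section 20) | Cardiac comorbidities recorded |

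The data form does not settle the matter. It also lists atrial fibrillation and morbid obesity, while 7.2 excludes atrial arrhythmia and severe obesity, so a condition on the form is not necessarily eligible. Neither cardiac history nor underlying cardiac disease is defined. A patient admitted in cardiogenic shock, with no earlier cardiac history and no acute coronary syndrome, might pass section 1. The cardiac group is therefore few or possibly none, not certainly zero.

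**The plan's sample size**

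Section 4 gives two-sided alpha 5%, power 80%, n = 346, and "a minimum ratio that has an estimated clinical significance with a correlation coefficient of 1.5". A correlation cannot exceed 1, and atanh(1.5) is undefined. With r = 0.15:

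n = ((1.960 + 0.8416) / atanh(0.15))² + 3 = (2.8016 / 0.1511)² + 3 = 346.6

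This agrees with the stated 346, so I take 0.15 as the intended value. The sample size covers the overall correlation only, not objective 2.

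**Two-group comparison (objective 2 as worded)**

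The difference detectable with 80% power, in SD units, is 2.8016 × √(1/n1 + 1/n2), with n1 + n2 = 346. The values of n1 are assumptions, because the documents give none.

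| Rule applied | n1 with cardiac disease | n2 | Detectable difference (SD) |
|---|---|---|---|
| Section 1 | 5 | 341 | 1.26 |
| Section 1 | 10 | 336 | 0.90 |
| Section 1 | 20 | 326 | 0.65 |
| Section 7, 10% | 35 | 311 | 0.50 |
| Section 7, 20% | 69 | 277 | 0.38 |
| Section 7, 30% | 104 | 242 | 0.33 |
| Section 7, 40% | 138 | 208 | 0.31 |
| Section 7, 50% | 173 | 173 | 0.30 |

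**Different response to pH (the hypothesis)**

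For a difference between two correlations on the Fisher z scale, SE = √(1/(n1−3) + 1/(n2−3)), and power is Φ(Δz/SE − 1.960). For 0.15 versus 0, Δz = 0.1511. For 0.30 versus 0, Δz = 0.3095.

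| Prevalence | SE | Power, 0.15 v 0 | Power, 0.30 v 0 |
|---|---|---|---|
| 10% | 0.186 | 13% | 39% |
| 20% | 0.137 | 20% | 62% |
| 30% | 0.119 | 25% | 74% |
| 40% | 0.111 | 28% | 80% |
| 50% | 0.109 | 29% | 81% |

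Correlations stand in for slopes here only if the spread of pH change and the residual variance are similar in both groups.

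**Can the two-group test mislead?**

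Assume groups of 104 and 242, the same slope in both, residual SD 1, and pH change with SD 1. With slope 0.30 and mean pH change differing by 1 SD, the outcome means differ by 0.30. The outcome SD is √(1 + 0.09) = 1.044 and SE = 1.044 × √(1/104 + 1/242) = 0.122. Then z = 2.45, and the test rejects about 69% of the time although the response to pH is identical.

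Simulation with 4000 runs per scenario gives:

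| Slope | Difference in mean pH change | t test rejects | Product term rejects | Disease term, adjusted for pH change, rejects |
|---|---|---|---|---|
| 0.30 | 1 SD | 68% | 5.7% | 5.4% |
| 0.30 | 0.5 SD | 24% | 5.0% | 4.6% |
| 0.15 | 1 SD | 24% | 4.6% | 5.2% |
| 0.15 | 0.5 SD | 10% | 4.8% | 4.8% |

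**The case against.** The strongest reply is that the exclusion is one sentence in an introductory passage written for patients and the public. Every section that sets eligibility agrees without it, and the hypothesis, objective 2 and the data form (which also lists pacemakers, resynchronisation devices and cardiothoracic surgery) point to cardiac patients being enrolled. On this view the sentence is a stray. That may well be so, but nothing in the protocol says section 7 overrides section 1, the sentence is worded as a rule, and a stray rule still has to be removed. That different sites would read it differently is a risk, not something the documents show.

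It is also fair that the group sizes of 5, 10 and 20 are illustrative. They show how precision falls in a small group and do not predict enrolment.

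On the secondary point, section 8 allows multiple regression with several predictors. Entering pH change and cardiac disease together brings false rejection back to about 5% with no interaction term, as the last column above shows. This stands. However, the plan neither names cardiac disease as a covariate nor guarantees that it stays in the model, and that model still does not test whether cardiac disease modifies the response. Objective 2 as worded does not strictly require such a test; the hypothesis does. The interaction term therefore ranks below the eligibility conflict, and its low power is a reason to report it with its uncertainty.

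**Conclusion.** The concern holds and must be fixed. The conflict between section 1 and primary objective 2 is in the text and needs no assumption. Under section 1 the cardiac-disease group would be largely or wholly absent. Under section 7 the objective as worded can be estimated.

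The size of the loss depends on group sizes that the documents do not give. Across the assumed values, the detectable difference is 0.65 to 1.26 SD in the first case and 0.30 to 0.50 SD in the second.

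The missing term for pH change by cardiac disease is a real but secondary gap. With 346 patients, power for correlations of 0.15 versus 0 is only about 13% to 29%, and 39% to 81% for 0.30 versus 0. These figures rest on assumed prevalence and on reading the printed 1.5 as 0.15.

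**What to change.** Before data collection, reconcile section 1 with objective 2 and section 7, so that one eligibility rule applies at all seven ICUs. There are three consistent routes, and the choice is the sponsor's:

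1. Remove the exclusion from section 1.
2. List it in 7.2 and withdraw objective 2.
3. Define cardiac history and underlying cardiac disease so that they differ and enough patients remain for the comparison.

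Unless objective 2 is withdrawn, state which data-form items define underlying cardiac disease, given that 7.2 already removes arrhythmia and valve insufficiency. In the same edit, bring the acid-base requirement in section 1 into line with 7.1, which omits it.

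If cardiac patients are enrolled, add a pre-specified product of pH change and cardiac disease to the estimative model in section 8. Keep it, with both main effects, regardless of the covariate-removal rules. Report the pH slope with its 95% confidence interval in each group, and state that 346 was not sized for this contrast. Say whether type of acid-base abnormality, the other modifier named in the hypothesis, will be handled the same way or not tested.

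The cost is some protocol wording, two definitions and one model term, since the form already collects the cardiac items. The drawback is an imprecise interaction estimate, which must be reported as such.
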